#### STUDY DESCRIPTION

#### 1. Title of the study

Evaluation of Therapeutic Potential of Stromal Vascular Fraction (Autologous Adipose Derived Mesenchymal Stem Cell) Based Treatment for Chronic Kidney Disease

#### 2. Introduction

#### 2.1 Chronic Kidney Disease (CKD)

CKD is a disease of alarmingly increasing prevalence (8 to 16%) associated with mortality [1]. CKD can progress towards end-stage renal disease (ESRD), requiring renal replacement therapy. ESRD currently accounts for 6.3% of the medicare spending in the United States, and is projected to increase by 85% by 2015 [2]. In a study conducted among rural population in Bangladesh overall CKD prevalence was found about 19% [3]. Furthermore, ESRD has a major impact on quality of life and life expectancy [4]. Therefore, it is very important to develop therapeutic interventions to prevent, alleviate, or decelerate progression of renal failure.

Diabetes mellitus and hypertension represent major causes of CKD and initiation of dialysis [5]. In addition, glomerular diseases, malnutrition, infectious diseases, and acute kidney injury can progress to ESRD, contributing to the increased global burden of death [6]. Current treatment modalities often fail to target the major underlying contributors for progression of renal disease [7]. Management of CKD at present mostly aims at control of the predisposing factors and supplementation of kidneys homeostatic functions but not at the treatment of the diseased kidney itself. Again due to lack of adequate facilities or financial constraints people of a developing country like Bangladesh are unable to continue long term or lifelong dialysis. Chronic glomerular and tubule-interstitial fibrosis is a common pathway to ESRD, often associated with apoptosis, oxidative damage, fibrosis and microvascular rarefaction. Unfortunately, the regenerative potential of kidney is limited under chronic conditions and inefficient to prevent progressive glomerulosclerosis and tubule-interstitial fibrosis [8]. Treatment strategies that boost cellular regeneration might therefore offer good alternatives for patients with CKD.

In the western world as well as in Bangladesh, high blood pressure and type II diabetes are on the rise and are contributing to higher rates of kidney disease. Demand for kidney transplants is increasing. But there are not enough donor organs to meet this growing need. So, cell based therapies may offer an alternative solution.

#### 2.2 Stromal vascular fraction (SVF)

SVF of adipose tissue is a rich source of pre-adipocytes, mesenchymal stem cells (MSC), endothelial progenitor cell, T cells, B cells, mast cells as well as adipose tissue macrophages [9,10]. SVF is a component of the lipo-aspirate obtained from liposuction of subcutaneous tissue. Lipo-aspirate contains a large population of stem cells called adipose derived stem cells (ADSCs), which share a number of similarities with bone marrow stem cells, including the capacity for multilineage differentiation.

[figure not shown]

Figure 1: Stromal vascular fraction.

#### 2.3 Stem Cells

A stem cell is a generic term referring to any unspecialized cell that is capable of long-term selfrenewal through cell division but that can be induced to differentiate into a specialized, functional cell. Stem cells are generally two types, embryonic stem cells and adult stem cells. Adult stem cells can be obtained from many differentiated tissues including, but not limited to, bone marrow, bone, fat, and muscle. Obtaining adult stem cells also does not raise any ethical concerns. For most studies, the adult stem cell in question is actually a mesenchymal stem cell (MSC) or mesenchymal stromal cell. They are multipotent but not pluripotent, which means they can differentiate into some, or "multiple," but not all tissue types [11]. Stem cells that are harvested from the patient with the intention of administering them back to the same patient are termed autologous MSCs. MSC can also be isolated from the bone marrow (bmMSC), peripheral blood, connective tissue, skeletal muscle, dental pulp (dpMSC), umbilical cord wall (ucMSC), umbilical cord blood (cbMSC), amniotic fluid (afMSC) and all have been used in experimental settings to treat various types of renal diseases. An important feature of MSCs is their capacity to induce proliferation of renal glomerular and tubular cells, increasing cellular survival [12].

[figure not shown]

Figure 2: Sources of MSC used in experimental models of renal injury. Preclinical studies have shown that MSC used to treat renal diseases can be isolated from the following tissues: (A) tooth pulp, (B) kidney, (C) adipose tissue, (D) umbilical cord, (E) amniotic fluid, and (F) bone marrow.

#### 2.4 Advantages of adipose tissue-derived stem cells (ADSCs)

ADSCs are somatic stem cell population contained in fat tissue and have been shown to possess stem cell properties such as trans-differentiation and self-renewal [13]. Similar to other types of

MSCs, ADSCs express multiple CD marker antigens (CD73+CD90+CD105+ CD34+/- CD11b-CD104b- CD19- CD31- CD45- SMA-) [14,15]. Additionally, utilizing ADSCs is advantageous in that large quantities of stem cells are easily isolated using minimally invasive surgical procedures [16].

ADSCs are vascular precursor cells. Many studies have shown that SVF contains progenitor cells that are able to differentiate into endothelial cells and participate in blood vessel formation [17]. Additionally, a recent study demonstrated that SVF cells expressing both pericyte and mesenchymal markers reside in a peri-endothelial location and stabilize endothelial networks [17] Another study showed that ADSCs transplanted into an ischemic renal cortex preferentially migrate toward micro vessels where they differentiate into vascular smooth muscle cells [18]. Some trials on kidney transplant recipients as well as the one on FSGS and 2 on CKD patients include in their protocol the utilization of adMSC. Adipose tissue is an important source of MSC, with a frequency 100 to 1000 times higher than bmMSC. They also seem to possess a higher potential for angiogenesis or vasculogenesis [19].

#### 2.5 Kidney disease and mesenchymal stem cells

A number of different types of cells from the bone marrow have been tested in animals and in clinical studies for potential use in kidney disease. Amongst all the cells under investigation, MSCs have shown the most promising results to date as they help kidney cells to grow, inhibit cell death and encouraging the kidney's own stem cells to repair kidney damage [20].

#### 2.6 Clinical trials using mesenchymal stem cells for renal repair

Few clinical trials have tested safety and efficacy of MSCs for renal disease. Reinders and colleagues studied safety and feasibility in six kidney allograft recipients who received two intravenous infusions of expanded autologous bone marrow-derived MSCs [21]. Importantly, delivery of autologous MSCs was not associated with adverse events, nor did it compromise graft survival. Several clinical trials are currently underway to evaluate the therapeutic potential of autologous and allogeneic MSCs for treatment of renal diseases [22] Administration of both bmMSC and adMSC has demonstrated significant reno-protective effects including reduction of intrarenal inflammatory infiltrate, decreased fibrosis, and glomerulosclerosis [12]

# 2.7 How else could stromal vascular fraction (autologous adipose derived MSC) help tackle kidney disease?

MSCs possess unique immunomodulatory properties that ameliorate inflammation and immune responses, constituting a promising tool to facilitate renal repair. In recent years, experimental studies have uncovered the potential of MSCs to improve renal function in several models of CKD, and several clinical studies have indicated their safety and efficacy in CKD [22].

ADSCs could be incorporated into damaged tissues or organs which could give rise to new functional components and also exert potent anti-inflammatory, anti-fibrotic, or immunomodulation effects through paracrine or autocrine routes (via vascular endothelial growth factor, granulocyte/macrophage colony stimulating factor, stromal-derived factor-1alpha and hepatocyte growth factor) [23,24]. Interestingly, it is proposed that even apoptotic or dying ADSCs exhibit distinctive immunosuppressive properties [25]. ADSCs have been shown to possess stronger anti-inflammatory and immuno-modulating functions than bone marrow derived MSCs [26].

Villanueva et al. explored the effect of ADSCs on CKD by a single intravenous infusion of ADSCs on a nephrectomy induced CKD model of rats [27]. ADSC treatment was associated with reduced plasma creatinine, higher levels of epitheliogenic and angiogenic proteins, and improved renal function. Work by Hyun et al[28] illustrated the beneficial effects of ADSCs on improving renal function on a IgAN mouse model. Zhang et al.[29] found that repeated systemic administration of ADSCs attenuated proteinuria, glomerulus hypertrophy, and tubular interstitial injury in a DN rat model.

Currently, several Clinical trials have been uploaded in the NIH database, all aim to test mainly the safety of using MSC and their efficacy in treating CKD. Two of them propose the use of autologous bmMSC and two adMSC. A study conducted in Tehran, Islamic Republic of Iran, which was designed to provide confirmation of Mesenchymal stem cell therapy in CKD. There 18 months safety and efficacy of autologous MSC as a therapy for CKD total of 10 patients were conducted with I/V injection of high dose of  $2x10^6$  / kg of autologous MSC. Assessments were performed at 1,3,6,12 and 18 months after cell injections [30].

Another study conducted in Birmingham, Alabama, Rochester, Minnesota, Jackson, Mississippi, USA where stem cell product called "Mesenchymal stem cell" grown from person's own fat tissue infused back in to the patient's own kidney and primary outcome measured after 3 months where renal tissue oxygenation increased and decrease in kidney inflammation was seen as secondary outcome [31].

#### 2.8 Route of delivery

Various routes for delivery of ADSCs, ADSC-induced cells, or ADSCs combined with compound materials have been developed for the treatment of different diseases or damaged tissue. These routes can be classified into two categories: systemic delivery through blood vessels (intravenous injection or intra-arterial injection) or local delivery directly into injured tissues or organs [32].

The route of MSC delivery may influence the cells' capacity to home and engraft the damaged tissue, and thereby their efficacy for renal repair. Commonly used experimental methods to deliver MSCs include systemic intravenous, intra-arterial, or intra-parenchymal delivery. In nonhuman primates the cells distribute broadly into the kidneys, skin, lung, thymus, and liver with estimated levels of engraftment ranging from 0.1 to 2.7% [33].

The route of MSC delivery, intravenous, intra-arterial, or intra-parenchymal, may affect their efficiency for kidney repair. When labeled MSC intravenously infused into baboons were observed for 9-21 months, estimated levels of engraftment in the kidney, lung, liver, thymus, and skin ranged from 0.1-2.7% [33] Indeed, the intravenous route lags in delivery efficiency, because MSC may initially be trapped in the lungs[34] Intra-arterial infusion of MSC was the most effective route to achieve immunomodulation in rat kidney transplantation, possibly by avoiding lodging in the pulmonary circulation, allowing MSC to home to the injured kidney [35].

An important feature of MSCs is their capacity to induce proliferation of renal glomerular and tubular cells, increasing cellular survival. By secreting proangiogenic and trophic factors, injected MSCs not only can enhance proliferation, but also can decrease apoptosis of tubular cells [36]. Several routes of administration (intra-parenchymal, sub-capsular, intravenous) have

been explored and all seem to be effective. Multiple, repeated injections of MSCs appear to be even more effective than single injections [37,38].

#### 2.9 Conclusion

Time has come to rethink about newer treatment approaches for increasing burden on haemodialysis and renal transplantation for CKD. MSCs have been shown to help avoid and reduce dialysis. It allows patients to work and continue life as productive citizens and also lessens dependency on family members by regaining independence. The financial benefits of eliminating dialysis and its consequences greatly outweigh the costs of stem cells. The long-term expense of dialysis is replaced by a short protocol of MSCs from SVF, which in all likelihood will eventually be a covered benefit of some insurance plans.

3. Objectives of the Study

3.1 General Objective

To assess the outcome of stromal vascular fraction (autologous adipose derived mesenchymal

stem cell) based treatment as a new, safe and minimal invasive modality for the treatment of

chronic kidney disease.

3.2 Specific Objectives:

(i) To assess the safety of stromal vascular fraction (autologous adipose derived mesenchymal

stem cell) in the treatment of CKD

(ii) To determine the role of SVF in treating different stages of CKD

(iii) To see if SVF can reverse or limit the progression of CKD

4. Methodology

The study will be conducted considering following methodological aspects.

4.1 Study design

Study Type: Interventional.

Primary Purpose: Treatment

Study Phase: Phase 1/Phase 2

Interventional Study Model: Parallel Assignment

Participants will be placed in either of the 2 groups, depending on

the number of harvested total stem cell count.

Those having a harvested total "Adipose Derived Stem Cell

(ADSC)" count (in 5 ml SVF solution) between 1 x 10^6 to 2 x

10^6 will be placed in "Group A".

13

Those having a harvested total "Adipose Derived Stem Cell (ADSC)" count (in 5 ml SVF solution) more than 2 x 10^6 will be placed in "Group B".

Both groups will be studied for Phase I/ Phase II trial by the proposed outcome measures over the stipulated time frame.

Those having a harvested total "Adipose Derived Stem Cell (ADSC)" count (in 5 ml SVF solution) less than 1 x 10^6 will be excluded from the study.

Number of Arms: 2

Masking: Triple (Participant, Care Provider, Outcomes Assessor)

Allocation: Non-Randomized

Enrollment: 31 [Anticipated]

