#### 4.2 Arms and Interventions

Arms: Participants having a harvested total "Adipose Derived Stem Cell (ADSC)" count (in 5 ml SVF solution) between 1 x 10^6 to 2 x 10^6 will be placed in "Group A".

Participants having a harvested total "Adipose Derived Stem Cell (ADSC)" count (in 5 ml SVF solution) more than  $2 \times 10^6$  will be placed in "Group B".

Interventions: Both group A and Group B will be injected intravenously with harvested 5 ml of SVF containing Autologous Non Expanded ADSC and outcome will be observed over the period of 1(one) year.

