#### 4.8 Eligibility criteria

#### 4.8.1 Inclusion criteria

A patient is eligible for the study if all of the followings apply:

- a) Aged 18-80 years (inclusive)
- b) With chronic kidney disease (CKD)stage 3 to 5 (eGFR 60 to 0 mL/min/1.73m2 (inclusive)) Note: eGFR = estimated glomerular filtration rate
- c) Having provided informed written consent.

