#### 4.9 Treatment allocation

All subjects would be submitted for Stromal Vascular Fraction (Autologous Adipose Derived Mesenchymal Stem Cell) Based Treatment for Chronic Kidney Disease

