#### 7 **Procedure**

After harvesting the abdominal adipose tissue via liposuction SVF (stromal vascular fluid) are collected. Subsequently these are centrifuged in UNISTATIONTM, a centrifuge machine specifically manufactured for this purpose. Later it is mixed with collagenase solution and fat is separated. Stem cells containing SVF is collected after centrifugation. SVF is neutralized and washed with normal saline. Then it is washed with patient's own serum and normal saline. A sample is collected for cell counting by **Luna automated cell counter**. The final SVF is ready for subcutaneous or IV injection if 80-90% of cell remain viable, active and mobile.

As it is a closed door automatic procedure within a same machine, so after collection of 40ml of sub-cutaneous fat, all procedures are automated. So there is no chance of contamination. Steps are mentioned below.

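### Section 4.1 claims triple masking, but every patient knowingly receives SVF, so the before-after comparison that the trial is sized for is open label

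*Combined protocol and SAP*

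**What the plan says.** Section 4.1 (Study design) lists two arms, parallel assignment, "Allocation: Non-Randomized" and "Masking: Triple (Participant, Care Provider, Outcomes Assessor". The groups are formed by the harvested cell count: A from 1 × 10^6 to 2 × 10^6, B above that.

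The treatment is the same in both. Section 4.2 (Arms and Interventions): "Both group A and Group B will be injected intravenously with harvested 5 ml of SVF containing Autologous Non Expanded ADSC". Section 4.9 (Treatment allocation): "All subjects would be submitted for Stromal Vascular Fraction".

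Patients know what they receive. Section 4.8.1 (Inclusion criteria) requires "Having provided informed written consent", and section 7 (Procedure) begins "After harvesting the abdominal adipose tissue via liposuction SVF (stromal vascular fluid) are collected".

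In section 4.11.1 (Primary Outcome Measure), Phase II outcomes (b), (c) and (d) are all changes from baseline to week 24: renogram GFR with split function, creatinine-based eGFR, and need for dialysis in CKD 5. The last is a 0 to 7 score of the interval between dialysis sessions. Section 4.6 (Sample size determination) uses the standard deviation of a change. Section 4.13 (Data collection procedure) has the researcher interview patients face to face.

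**The concern.** Masking protects a comparison only if the people who could influence the outcome do not know which side of the comparison an observation belongs to. Here the comparison is week 24 against week 0 in the same patients, all of whom have been treated in between. Hiding whether a patient is in Group A or Group B does nothing for it.

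A report that repeated the label in section 4.1 would lead readers to treat the Phase II efficacy results as triple masked. That would overstate their freedom from bias, above all for dialysis need. That outcome scores how often dialysis is given, with no stated criterion for need and no masked assessor.

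**Working it through.** **1. Which comparison is the trial sized for?** Inputs from section 4.6: two-sided alpha 0.05 (z = 1.960), beta 0.20 (z = 0.842), E = 0.5, SD of the change = 1.0.

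- One-sample change: N = (1.960 + 0.842)² / (0.5/1.0)² = 7.849 / 0.25 = 31.4. The plan states about 31, so its figure is reproduced (rounding up would give 32, which does not matter here).
- Group A against Group B at the same 0.5 SD: 2 × 7.849 / 0.25 = 62.8, so 63 per group. This does not match.

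The stated N is a before-after calculation on the whole cohort, with no between-group term.

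**2. What could be masked?**

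| Fact | Could it be hidden? | Where |
|---|---|---|
| Receipt of SVF | No: all consent, have liposuction and are injected; no sham or untreated group | 4.2, 4.8.1, 4.9, 7 |
| Before or after treatment | Not from patient or carer; from a scan reader only if scans are coded, which is not described | 4.11.1, Annexure D |
| Group A or B | Possible in principle: same volume, same route | 4.1, 4.2 |

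For the A/B group, the text available does not say who holds the count or from whom it is withheld. The counting sample is drawn just before injection (section 7, final step), and a count below 1 × 10^6 excludes the patient (section 4.8.2). Someone at the procedure may therefore see the figure, so concealment needs a described procedure.

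**3. How much could the maskable comparison carry?** Power for a 0.5 SD difference, SD 1.0, two-sided 5%, 31 patients in all:

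- 15/16 split: 0.5 / √(1/15 + 1/16) = 1.391; Φ(1.391 − 1.960) = 0.28.
- 5/26 split: 0.5 / √(1/5 + 1/26) = 1.024; Φ(1.024 − 1.960) = 0.17.

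The split is not known in advance, because the harvest decides it.

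**4. What could bias do to the comparison that is not masked?** The documents give no bias size, so b = 0.1 to 0.3 SD is an assumed range. With no true effect and n = 31, the test rejects with probability 1 − Φ(1.960 − b√31) + Φ(−1.960 − b√31), where √31 = 5.568.

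| b (SD) | b√31 | Probability of rejecting |
|---|---|---|
| 0 | 0 | 0.05 |
| 0.1 | 0.557 | 0.086 |
| 0.2 | 1.114 | 0.20 |
| 0.3 | 1.670 | 0.39 |

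A t-test gives 0.084, 0.19 and 0.37 for the last three rows. These figures describe a whole-cohort outcome at n = 31. They do not apply to dialysis need, which is measured only in the CKD 5 patients, whose number is not given.

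**5. Are the outcomes equally exposed?** No.

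- Dialysis need (d): scored from the interval in use, without a criterion or a masked assessor, on a clinical form completed at every visit (Annexure C, Questionnaire 1). Most exposed.
- Renogram GFR and split function (b): a measurement. How and by whom scans are read is not stated, so exposure cannot be judged.
- Creatinine-based eGFR (c): calculated from a laboratory value. Little room for an assessor's judgement.

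**The case against.** The masking entry stands beside two arms and parallel assignment, where it is naturally read as hiding Group A from Group B. Both groups receive the same volume by the same route, so that is feasible, and nowhere does the plan say that the before-after change is masked. On this reading the line needs a qualifier and is not simply false. That stands. It does not rescue the label, because the qualifier is absent, no procedure is described, and A against B is not what the sample size supports.

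Three stronger readings are tempting, and the documents do not support them:

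- That a renogram reader who knows the visit draws the regions. Section 4.11.1 and Annexure D name the test and its values but no reader, method or state of knowledge.
- That clinician or patient decides the dialysis interval. It is plausible, but section 4.11.1 only scores the interval and does not say who sets it.
- That all the before-after outcomes are compromised alike. Creatinine-based eGFR is not open to assessor bias in the way dialysis need is.

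A numerical bias for the dialysis score is likewise not available. Saying that a share p of CKD 5 patients shifts one step, and so the mean shifts by p, only restates the assumption. Patients who score 0 at baseline could not improve at all.

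**Conclusion.** The concern holds as a mismatch between a stated design property and the comparison on which the trial relies. Receipt of SVF is known to all, so the Phase II before-after comparison is open label. Masking could apply at most to the A/B cell-count group. The plan does not say how that would be kept, and power for that contrast is at most about 28% at 0.5 SD.

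The bias argument is strongest for dialysis need, weak for creatinine-based eGFR, and undetermined for the renogram. The rise in false positives from 5% to between about 9% and 39% rests wholly on the assumed 0.1 to 0.3 SD. It shows how sensitive a one-sample test of this size is and does not estimate bias in this trial. A reader should not infer that the results will be biased by a known amount, or that concealing A from B is impossible.

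**What to change.** - Restate section 4.1 as open label for receipt of SVF.
- Claim masking only for the A/B count group, and only if section 4.1 says who holds the count and from whom it is withheld. Otherwise drop the claim.
- Have whoever already reads the DTPA renograms do the research read with patient and visit coded and the scans in shuffled order. Batch weeks 0 and 24 for primary outcome (b), so that its result does not wait for week 48. The week 48 scans in Annexure D are not part of that outcome and can be read later.
- State in section 4.11.1, and in any report, that dialysis need is an unmasked outcome.

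This adds no patients, tests, arms or readers, and changes nothing in clinical management. The cost is a less favourable masking statement and some coding and batching of scans for the research read. Coded reading limits reader bias only. It does not stand in for a control group.
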